4. OBJECTIVES AND OUTCOME MEASURES

Objectives	Outcome Measures	Timepoint(s) of evaluation of this outcome measure ^a		
Primary Objective				
To identify biomarkers of exposure to bites of Southeast Asian mosquito vectors of malaria and dengue.	1) Levels and kinetics of specific antibody titers against candidate peptides before and during repeated exposure to bites of laboratory-reared Anopheles minimus, An. maculatus, An. dirus, Aedes aegypti and Ae. albopictus determined by ELISA and mesoscale screening.	1) Day 0, 7 (baseline), 14, 21, 28, 35, 42, 49, 56 (exposure period), 63, 70, 77, 84, 91, 98, 105 and 112 (post-exposure period).		
	2) Sequence of saliva antigens determined with an immuno-proteomic method (2D gel electrophoresis of salivary gland protein extracts, Western blot and mass spectrometry).	2) Day 14 (baseline), 63 and 112 (post-exposure period).		
Secondary Objectives				
1) To characterize the relationship between levels of mosquito exposure and humoral response.	Comparison of the antibody titers determined in subgroups corresponding to different level of exposure.	Day 0, 7 (baseline), 14, 21, 28, 35, 42, 49, 56 (exposure period), 63, 70, 77, 84, 91, 98, 105 and 112 (post-exposure period).		
2) To assess the feasibility of using dry blood spots made from capillary blood for the monitoring of exposure to bites of mosquito vectors of malaria and dengue.	Comparison of the antibody titers determined in DBS and venous blood samples.	Day 0, 7 (baseline), 14, 21, 28, 35, 42, 49, 56 (exposure period), 63, 70, 77, 84, 91, 98, 105 and 112 (post-exposure period).		

^a See Appendix C.

DBS: dry blood spots; ELISA: enzyme-linked immunosorbent assay.

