each of the study condition (Appendix B). Participants will be in the study for 112 days (Appendix C). The baseline will consist of 2 visits over 2 weeks (day 0 and day 7). In the low-exposure groups, participants will be exposed to 5 mosquito bites at weekly intervals from day 14 to day 56 (seven challenges with 5 mosquito bites/challenge over six weeks, yielding a total of 35 mosquito bites). In the high-exposure group, participants will be exposed to 5 mosquito bites on day 14 and then to 50 mosquito bites at weekly intervals from day 21 to day 56 (one challenge with 5 mosquito bites and six challenges with 50 mosquito bites/challenge over 6 weeks, yielding a total of 305 mosquito bites). The number of bites and modalities of the follow up used in this study were chosen based on previous entomological investigation conducted in this area (10, 11, 96), published reports of human challenge with mosquito bites (37, 97-99) and current knowledge on the characteristic of the humoral response against saliva antigens (31, 37, 52). Both immediate and delayed skin reactions will be recorded after day 14 and day 21 challenges, requiring additional visits at day 15 and day 22. Participants with hypersensitivity to mosquito bites will be withdrawn from the study. Both capillary and venous blood samples will be collected weekly from each study participant (Appendix D). Eighteen venous blood samples will be collected including one sample of 2 mL drawn during screening visit, 14 samples of 8.6 mL during visits 2, 3, 6, 8, 9, 10, 11, 12, 14, 15, 16, 17, 18 and 19, and 3 samples of 18.6 mL during visits 4, 13 and 20 (178.2 mL of venous blood per participant in total). Seventeen dry blood spot (DBS) samples will be made from of 300 uL of capillary blood collected during visits 2, 3, 4, 6, 8, 9, 10, 11, 12, 13, 14, 15, 16, 17, 18, 19 and 20 (5.1 mL of capillary blood per participant in total). Candidate peptides will be identified in silico using publicly available genomes sequences and B-cell epitope prediction algorithms. The kinetic of antibody titers against candidate biomarkers will be assessed by enzyme-linked immunosorbent assay (ELISA) and mesoscale screening performed with serum and DBS specimens (100). Briefly, the positivity threshold of the assay will be determined using reference sera specimens from individuals not exposed to mosquito bites, as described previously (62). The ELISA signal measured in 60 reference sera obtained from unexposed individuals (30 Thai sera obtained from the Thai Red Cross and 30 Australian sera obtained from the Burnett Intstitute) will be used to define the positivity threshold of the assay. The positivity threshold of the assay will be defined as three standard deviation (SD) above the mean optic density (Δ OD) measured for the unexposed control population. A test in the study population with a ΔOD above this cut-off will be considered positive (i.e. an immune response). The specific antibody titer of study samples will be determined by performing serial dilution experiments (101). Serial dilution will be made from study samples and the Δ OD will be determined for each dilution. The antibody titer will be defined as the highest dilution giving a positive signal. Results obtained with DBS and serum specimens will be compared in order to assess the feasibility of using DBS samples to monitor exposure to bites of mosquitoes during epidemiological studies. Serum specimens collected during visits 4 (baseline), 13 (early after the end of exposure) and 20 (post-exposure) will also be analysed with immuno-proteomic approach (2D gel electrophoresis of salivary gland protein extracts, Western blot and mass spectrometry) yielding additional information on the antigenic properties of mosquito salivary gland proteome (102).

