Two-dimensional gel electrophoresis will be performed with protein extracts made from the dissected salivary glands of 200 female adult mosquito specimens. In order to obtain a sufficient resolution, protein separation will be done on an 11 cm × 20 cm gel format. The gel proteins will be then transferred to a membrane. The membrane will be incubated with 50 mL of serum diluted 10 folds (5mL of neat serum) in order to assess the reactivity of serum IgG by Western blot (53). Reactive spots of interest will be detected by comparing the staining patterns from baseline, end of exposure and post-exposure samples. Spots of interest will be excised from the 2D gel and used to perform in gel digestion with trypsin. The protein digest will be analysed with liquid chromatography-mass spectrometry. Immunogenic proteins will be identified by searching the mass spectra with Mascot (Matrix Science Ltd.).

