15		77	No	No	No	No	No	Yes	Yes
16	post-	84	No	No	No	No	No	Yes	Yes
17	exposure	91	No	No	No	No	No	Yes	Yes
18		98	No	No	No	No	No	Yes	Yes
19		105	No	No	No	No	No	Yes	Yes
20		112	No	No	No	No	No	Yes	Yes

19. APPENDIX C: Schedule of participant's visits including informed consent blood sampling and exposure to mosquito bites

^a In case participant fail to come on the exact day a visit is scheduled, he/she will be allowed to come for a retake any other working day of the study team until the next scheduled visit;

^b 5 bites for the screening of hypersensitivity to mosquito bites during visit 4, then 5 or 50 bites/visit according to the randomisation schedule (total of 35 and 305 bites/participant in low- and high-exposure groups respectively, split into 7 direct feeding assays);

^c before exposure to mosquito bites.

^d 2 mL during the screening visit, 8.6 mL during visits 2, 3, 6, 8, 9, 10, 11, 12, 14, 15, 16, 17, 18 and 19 and 18.6 mL during visits 4, 13 and 20.

Period	Visit no.	Day	Venous blood (ml)	Total volume of serum (ml)	Volume of serum sent to BI (ml) ^a	Volume of serum sent to A*STAR (ml) ^b	Volume of serum sent to WRAIR (ml) ^c	Capillary blood (ml)		
Screening	1	30 days or less before enrolment	2	NA	NA	NA	NA	0		
Baseline	2	0	8.6	4.1	2	2	0.1	0.3		
	3	7	8.6	4.1	2	2	0.1	0.3		
Exposure	4	14	18.6	9.1	7	2	0.1	0.3		
	5	15	0	NA	NA	NA	NA	0		
	6	21	8.6	4.1	2	2	0.1	0.3		
	7	22	0	NA	NA	NA	NA	0		
	8	28	8.6	4.1	2	2	0.1	0.3		
	9	35	8.6	4.1	2	2	0.1	0.3		
	10	42	8.6	4.1	2	2	0.1	0.3		
	11	49	8.6	4.1	2	2	0.1	0.3		
	12	56	8.6	4.1	2	2	0.1	0.3		
Post- exposure	13	63	18.6	9.1	7	2	0.1	0.3		
	14	70	8.6	4.1	2	2	0.1	0.3		
	15	77	8.6	4.1	2	2	0.1	0.3		
	16	84	8.6	4.1	2	2	0.1	0.3		
	17	91	8.6	4.1	2	2	0.1	0.3		
	18	98	8.6	4.1	2	2	0.1	0.3		
	19	105	8.6	4.1	2	2	0.1	0.3		
	20	112	18.6	9.1	7	2	0.1	0.3		
Total			178.2					5.1		
		Grand Total	Grand Total for Blood collection = 183.3 mL							

20. APPENDIX D: Summary of blood volumes drawn from participants

^a Samples sent to the Burnet Institute (BI) will be used for ELISA screening and immuno-proteomic analysis;

^b Samples sent to the Singapore Immunology Network, Agency for Science, Technology, and Research, Singapore (A*STAR) will be used for ELISA screening;

^c Samples sent to the Walter Reed Army Institute of Research (WRAIR) will be used for mesoscale screening.

Abbreviations: NA, not applicable.

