8.2 Derived Variables

The following measures will be derived:

- Linear splines will be derived using the visit variable to represent the baseline (visits 2-3), exposure to *Anopheles* spp. bites (visits 4-12) and post exposure (visits 13-20) periods to model the boosting and decay of antibody responses.
- Exposure and post-exposure periods will be derived as a categorical time-varying variable.
- Concordant and discordant exposure species and antibody responses variables will be derived by collapsing across categories of the mosquito species participants were exposed to, according to the following groups: (i) exposure to *Anopheles* spp. compared to *Aedes* spp. (explored for all anti-SG6-P1 antibodies), (ii) exposure to *An*.

dirus bites, compared to *An. maculatus* and *An. minimus* bites, compared to *Aedes* spp. bites (explored for anti-dirSG6-P1 antibodies), (iii) exposure to *An. maculatus* bites, compared to *An. dirus* and *An. minimus* bites, compared to *Aedes* spp. bites (explored for anti-macSG6-P1 antibodies), (iv) exposure to *An. min* bites, compared to *An. maculatus* and *An. dirus* bites, compared to *Aedes* spp. bites (explored for anti-minSG6-P1 antibodies).

8.3 **Protocol Deviations**

The following will be considered as protocol deviations:

- Variation of Inclusion/Exclusion criteria
- Significant protocol deviations, which may have an effect on the integrity of study data

Protocol deviations were reviewed prior to un-blinding to determine which protocol deviations may affect the analysis. The Per Protocol Set will then be defined for the antibody endpoints with the following exclusions:

- Data from all available visits for subjects found to violate inclusion/exclusion criteria.
- Data from all visits subsequent for the protocol deviations that are considered to affect the integrity of the antibody data.
- Data from any visit that occurs substantially out of window.

Protocol deviations will not be excluded from the Intention to Treat Set, but may result in subjects being excluded from the Per Protocol Set. After review of the data prior to unblinding, no subjects were excluded from the Per Protocol Set.

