9.1 Effect of mosquito biting exposure on antibody level and seropositivity

Measurement of mosquito species-specific antibodies will be using high-throughput ELISA are described in Table 3:

Assay	Visits	Outcomes
High-throughput ELISA	Visits 2-	Total Anti-IgG levels and seropositivity against:
	20	gSG6-P1
		minSG6-P1
		macSG6-P1
		dirSG6-P1
		aegNterm34kDa

Table 3 Overview of assays

Assay	Visits	Outcomes
		albNterm34kDa
High-throughput ELISA	Visits 2-	Total Anti-IgM levels and seropositivity against:
	20	gSG6-P1
		minSG6-P1
		macSG6-P1
		dirSG6-P1
		aegNterm34kDa
		albNterm34kDa
High-throughput ELISA	Visits 2-	Total antibody (including any isotype or subclass)
	20	levels and seropositivity against novel candidate
		Anopheles and Aedes species-specific antigens

Antibody markers will be summarised at each scheduled time point, including changes from baseline. Values will be presented visually with dotplots at each time point and spaghetti plots to visualise within-participant changes from baseline.

The change in antibody levels (as a continuous outcome and binary response) over time will be analysed using generalised linear mixed-effects models. Optical density measurements (*i.e.* antibody levels) will be analysed using a Gaussian distribution family and identity link function (*i.e.* a linear mixed-effects model) and binary responder status will be analysed using a Binomial distribution family and a logit link function (*i.e.* a logistic mixed-effects model). Linear splines will be fitted to represent the baseline (visits 2-3), exposure to mosquito bites (visits 4-12) and post exposure (visits 13-20) periods to model the boosting and decay of antibody responses. Mixed-effects models will include a random effect (*i.e.* intercept) for participant to allow random variations of immune responses in individuals. Estimates from the linear mixed-effects models will be used to calculate the half-lives of each antibody measure.

Amendment to SAP 23/03/2023

To account for positively skewed antibody data and aid interpretation, antibody levels were log₂ transformed to represent a two-fold change in antibody levels.

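### The visit 13 sample is the first that can show the seventh challenge but is coded as post-exposure; report the exposure effect and the half-life under a lagged coding as well

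*Protocol*

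**What the plan says.** **Schedule.** Challenges run weekly from day 14 to day 56. Protocol section 5 gives the low-dose arms "seven challenges with 5 mosquito bites/challenge over six weeks, yielding a total of 35 mosquito bites" and the high-dose arms "one challenge with 5 mosquito bites and six challenges with 50 mosquito bites/challenge over 6 weeks, yielding a total of 305 mosquito bites". The seventh challenge is at visit 12 (day 56).

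**Sampling.** Note c to the visit table in Protocol Appendix C says that blood is taken "before exposure to mosquito bites". The note stands on the venous sampling column heading, so it covers every challenge visit. The SAP's Table 2 carries it only on the visit 4 cells. Protocol 7.3 lets a missed visit be retaken up to the next scheduled visit.

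**Period coding.** Protocol section 4 lists days "49, 56 (exposure period), 63, 70, 77, 84, 91, 98, 105 and 112 (post-exposure period". SAP 8.2 puts exposure to "bites (visits 4-12) and post exposure (visits 13-20) periods to model the boosting and decay of antibody responses", and SAP 9.1 repeats these ranges. The amendment of 23 March 2023 drops the linear splines. It fits exposure and post-exposure as a categorical time-varying variable in a GEE, with period-by-time interactions and an autoregressive correlation. It neither restates the visit ranges nor introduces a lag, and it does not say how the half-life is obtained from the new model.

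**Immuno-proteomic samples.** Protocol section 5 describes them as taken at "visits 4 (baseline), 13 (early after the end of exposure) and 20 (post-exposure". Protocol 7.7 describes the analysis as "comparing the staining patterns from baseline, end of exposure and post-exposure samples".

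**The concern.** An antibody sample reflects bites already received. With blood drawn before the bites, every sample from day 21 on first reads the challenge given a week earlier. The calendar coding ignores this lag, with two consequences.

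First, the exposure-period term contains no sample that can show the seventh challenge, and it does contain visit 4, which precedes every bite. This bears on the dose-response objective.

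Second, the post-exposure slope starts at visit 13. If responses are still rising 7 days after a bite, that slope includes a point at or before the peak, so decay looks slower and the half-life too long. The SAP preface lists half-life among the critical parameters not yet assessed precisely.

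**Working it through.** **1. The plan's own totals.** Low dose: 7 × 5 = 35. High dose: 5 + 6 × 50 = 305. Both match the documents.

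**2. Bites received before each sample** (scheduled days, blood before bites):

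| Day (visit) | 14 (4) | 21 (6) | 28 (8) | 35 (9) | 42 (10) | 49 (11) | 56 (12) | 63 (13) |
|---|---|---|---|---|---|---|---|---|
| Low | 0 | 5 | 10 | 15 | 20 | 25 | 30 | 35 |
| High | 0 | 5 | 55 | 105 | 155 | 205 | 255 | 305 |

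The seven exposure-coded samples (visits 4, 6, 8-12) therefore reach at most 30/35 = 85.7% or 255/305 = 83.6% of the bites. The seventh challenge is 5/35 = 14.3% or 50/305 = 16.4% of the total.

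Mean prior bites over exposure samples:
- Calendar coding: low 105/7 = 15.0; high 780/7 = 111.4.
- Visits 6 and 8-13: low 140/7 = 20.0; high 1085/7 = 155.0.
- Visit 13 added with visit 4 kept: high 1085/8 = 135.6. Correcting one boundary alone is a half measure.

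**3. Half-life.** The documents give neither a time to peak nor a decay rate, so both are assumed. Each challenge adds a response that rises linearly to a peak at L days and then falls as 2^(−(t−L)/H). The rise starts at day 0 or day 3, and challenges count equally or in proportion to bites. The seven responses are summed and log2-transformed. A straight line is then fitted by generalised least squares with AR(1) correlation between weekly samples (rho 0 to 0.95). Estimated half-life = −7/(weekly slope).

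One case by hand (equal responses, rise from day 0, L = 14, H = 28): the summed response is 4.56, 4.42 and 3.71 on days 63, 70 and 77. The log2 fall is log2(4.56/4.42) = 0.05 in the first week and log2(4.42/3.71) = 0.25 in the second. True decay is 7/28 = 0.25 per week, so day 63 is not yet on the decay line. Unweighted fits give 30.0 days from day 63 and 28.0 from day 70.

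Over the whole grid (H = 14, 28, 56 days), fitting from day 63:

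| Peak L | Overstatement of half-life | Least and most extreme cases |
|---|---|---|
| 5 or 7 days | 0% | none |
| 10 days | about 3-19% | 14 becomes 14.5; 56 becomes 66.4 |
| 14 days | about 6-31% | 14 becomes 14.8; 56 becomes 73.4 |

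Fitting from day 70 returns 14, 28 and 56 for every L up to 14 days. At L = 21, with equal responses, rise from day 0 and rho 0, the day 70 fit still gives 14.9, 29.9 and 61.6, which is 6-10% too long.

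**4. Precision cost of starting at visit 14.** With independent errors and n equally spaced points, the slope variance is proportional to 1/[n(n²−1)/12]. This sum is 42 for n = 8 and 28 for n = 7, so the standard error ratio is √(42/28) = 1.22. At rho 0.95 the ratio is 1.09.

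**The case against.** **The label is correct.** No bites are given at visit 13, so post-exposure is accurate by calendar. Defining periods by when bites are given is a legitimate choice. This stands: the point is about what the period terms can measure, not a coding error.

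**No data are lost.** The response to the seventh challenge enters the post-exposure term, and SAP 9.1 summarises and plots every visit. This also stands. The gap is confined to the exposure-period effect and slope.

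**A reader might infer that the protocol contradicts itself**, treating visit 13 as end of exposure in one primary outcome and as decay in the other. The documents do not support that. Protocol section 4 groups day 63 as post-exposure for both primary outcomes, and section 5 and the immuno-proteomic text in 7.7 both call visit 13 early after exposure. Only one later sentence in 7.7 uses the end-of-exposure wording.

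**The visit ranges appear only in the spline text, which has been superseded.** True. That they carry over to the amended model is an inference, but the amendment gives no other definition of the two categories.

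**The half-life bias is hypothetical.** It is zero for a peak by 7 days, and the 31% figure needs a 14-day peak, a 56-day half-life, strong serial correlation, a dose-proportional response and a delayed rise together. With equal responses, rise from day 0 and rho 0, the figures are about 4-6% at 10 days and 6-11% at 14 days. This is why visit 14 should not simply replace visit 13 as the only start: if the peak is early, that gives up precision for nothing.

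**Conclusion.** This is a cheap improvement, not an error in the plan. Two facts need no kinetic assumption beyond blood being drawn before the bites on schedule: no exposure-coded sample can reflect the seventh challenge, and one of the seven (visit 4) reflects no bites. Even blood drawn shortly after the day 56 bites could not yet show an antibody response to them.

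The half-life effect is conditional on a peak later than 7 days after a challenge, with the sizes shown in the working. A late retake of the seventh challenge would act in the same direction, because the visit 13 sample would then follow those bites by less than 7 days. A reader might infer that the half-life will be biased; the documents give no latency from which to conclude that.

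**What to change.** Amend SAP 8.2 and 9.1. SAP 5.1 records that the biostatisticians have been unblinded, so under SAP 7.1 this is a documented, post-hoc amendment.

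1. Estimate the half-life from visits 14-20 as well as from visits 13-20. Report both and state which is primary. State also how the half-life is derived from the amended GEE.
2. Alongside the calendar coding, report the exposure effect with samples coded by the bites they can reflect: visit 4 as baseline, visits 6 and 8-13 as exposure. Protocol section 4 already calls day 14 baseline for the immuno-proteomic outcome.
3. In Protocol 7.7, align the end-of-exposure wording with section 4, section 5 and the earlier text of 7.7.

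The cost is SAP wording and recoding of two visits, with no new samples or assays. The visit 14-20 slope has a standard error 9-22% larger, and some bias remains if the peak is as late as 21 days.

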5. STUDY DESIGN

A schematic diagram detailing the study design, procedures and stages step-by-step is presented in the Appendix A. This study is a human challenge model with five arms corresponding to controlled exposure to bites of uninfected laboratory-adapted colonies of *Anopheles minimus*, *An. maculatus*, *An. dirus*, *Aedes. aegypti* or *Ae. albopictus* (see sections 8 and 13.5.1). Following screening and eligibility assessment, 150 participants will be enrolled in the study using a block-randomized design stratified on the mosquito species and number of bites (35 or 305 bites in total) such as to constitute 10 groups of 15 individuals for

each of the study condition (Appendix B). Participants will be in the study for 112 days (Appendix C). The baseline will consist of 2 visits over 2 weeks (day 0 and day 7). In the low-exposure groups, participants will be exposed to 5 mosquito bites at weekly intervals from day 14 to day 56 (seven challenges with 5 mosquito bites/challenge over six weeks, yielding a total of 35 mosquito bites). In the high-exposure group, participants will be exposed to 5 mosquito bites on day 14 and then to 50 mosquito bites at weekly intervals from day 21 to day 56 (one challenge with 5 mosquito bites and six challenges with 50 mosquito bites/challenge over 6 weeks, yielding a total of 305 mosquito bites). The number of bites and modalities of the follow up used in this study were chosen based on previous entomological investigation conducted in this area (10, 11, 96), published reports of human challenge with mosquito bites (37, 97-99) and current knowledge on the characteristic of the humoral response against saliva antigens (31, 37, 52). Both immediate and delayed skin reactions will be recorded after day 14 and day 21 challenges, requiring additional visits at day 15 and day 22. Participants with hypersensitivity to mosquito bites will be withdrawn from the study. Both capillary and venous blood samples will be collected weekly from each study participant (Appendix D). Eighteen venous blood samples will be collected including one sample of 2 mL drawn during screening visit, 14 samples of 8.6 mL during visits 2, 3, 6, 8, 9, 10, 11, 12, 14, 15, 16, 17, 18 and 19, and 3 samples of 18.6 mL during visits 4, 13 and 20 (178.2 mL of venous blood per participant in total). Seventeen dry blood spot (DBS) samples will be made from of 300 uL of capillary blood collected during visits 2, 3, 4, 6, 8, 9, 10, 11, 12, 13, 14, 15, 16, 17, 18, 19 and 20 (5.1 mL of capillary blood per participant in total). Candidate peptides will be identified in silico using publicly available genomes sequences and B-cell epitope prediction algorithms. The kinetic of antibody titers against candidate biomarkers will be assessed by enzyme-linked immunosorbent assay (ELISA) and mesoscale screening performed with serum and DBS specimens (100). Briefly, the positivity threshold of the assay will be determined using reference sera specimens from individuals not exposed to mosquito bites, as described previously (62). The ELISA signal measured in 60 reference sera obtained from unexposed individuals (30 Thai sera obtained from the Thai Red Cross and 30 Australian sera obtained from the Burnett Intstitute) will be used to define the positivity threshold of the assay. The positivity threshold of the assay will be defined as three standard deviation (SD) above the mean optic density (Δ OD) measured for the unexposed control population. A test in the study population with a ΔOD above this cut-off will be considered positive (i.e. an immune response). The specific antibody titer of study samples will be determined by performing serial dilution experiments (101). Serial dilution will be made from study samples and the Δ OD will be determined for each dilution. The antibody titer will be defined as the highest dilution giving a positive signal. Results obtained with DBS and serum specimens will be compared in order to assess the feasibility of using DBS samples to monitor exposure to bites of mosquitoes during epidemiological studies. Serum specimens collected during visits 4 (baseline), 13 (early after the end of exposure) and 20 (post-exposure) will also be analysed with immuno-proteomic approach (2D gel electrophoresis of salivary gland protein extracts, Western blot and mass spectrometry) yielding additional information on the antigenic properties of mosquito salivary gland proteome (102).
